10.1.4 FUTURE USE OF STORED SPECIMENS AND DATA

Digital data collected for this study will be stored in OnCore and analyzed using an encrypted, password-protected server at the Yale School of Medicine. After the study is completed, the de-identified, archived data will be stored as described in Section 10.1.3, Confidentiality and Privacy.

The consent form for this study contains a section describing "Optional Specimens for Future Storage/Testing", and allows the individual being consented the option to allow or not allow their samples and information to be stored and used for future research. With the participant's indication of approval on the form, the samples will be used to research the role of soy isoflavones on inhibiting disease progression or controlling prostate cancer cell growth. This may help researchers in the future learn more about signaling pathways in tumor cells, treatment of prostate cancer, inflammatory diseases and other health conditions. Participants' stored material will not be shared beyond the investigative team of this study.

During the conduct of the study, even after agreeing to allow banking of their specimens, a participant may choose to withdraw consent to have their biological specimens stored for future research. However, withdrawal of consent with regard to biosample storage may not be possible after the study is completed.

10.1.6 SAFETY OVERSIGHT

The Yale Cancer Center (YCC) Data and Safety Monitoring Committee (DSMC) will provide the primary oversight of data and safety monitoring. The Yale DSMC will review and monitor compliance, toxicity and deviations from this study. The committee is composed of clinical specialists with experience in oncology and who have no direct relationship with the study. Information that raises any questions about participant safety will be addressed with the Principal Investigator.

The DSMC will review this protocol bi-annually, at a minimum. Information to be provided to the committee includes: a study narrative by the PI, a summary DSMC report produced by OnCore® (which includes participant accrual, response, trial status history, SAEs, adverse events, deviations and survival); audit results, and monitoring reports, as applicable. Other information (e.g., scans, laboratory values, etc.) will be provided upon request. Upon completing the review, the DSMC will approve whether the study should continue as planned, require modification/ amendment, or be placed on administrative hold with accrual temporarily suspended.

Trials being monitored by the YCC DSMC will remain under the YCC DSMC purview until a DSMC review has occurred that includes the research activity of the last subject who completed the intervention, or until the DSMC feels there are no patient safety concerns that require further monitoring. The DSMC will determine the length of continued DSMC review.

The DSMC has authority to intervene in the conduct of these studies as necessary to ensure the safety of the participants and to maintain the highest quality in the clinical research performed at YCC. The DSMC has the authority to require additional monitoring and/ or more frequent reporting on study progress and serious adverse events.

10.1.7 CLINICAL MONITORING

YCCI's assigned Study Monitor (Clinical Research Associate) will monitor all essential documents and data for timeliness of submission, completeness, and adherence to protocol requirements. Monitoring

will begin at the time of participant registration and will continue during protocol performance until study completion.

The principal investigator is responsible for monitoring the data, assuring protocol compliance, and conducting the safety reviews, formally at a quarterly basis. Safety data, however, is communicated to the investigators in real time. During the review process the principal investigator will evaluate whether the study should continue unchanged, require modification/amendment, or close to enrollment.

The principal investigator, the Yale University IRB, or the Yale Cancer Center Data and Safety Monitoring Committee have the authority to stop or suspend the study or require modifications.

10.1.8 QUALITY ASSURANCE AND QUALITY CONTROL

Under the direction of the Sponsor-Investigator the clinical trials manager will be responsible for addressing QA and QC issues and will oversee all activities related to study conduct according to the Yale IRB-approved application (HIC# 2000020868), and as stipulated in this protocol. The Yale Center for Clinical Investigation monitors participant accrual and status on study through OnCore®. All data changes to records are strictly audited. Examples of audit trail information available from the application include changes to subject demographics, changes to protocol status, and eCRF changes.

The laboratory-based study team will perform pathological investigations and assays required for the secondary endpoint analyses according to GLPs. All clinical and laboratory personnel on the study are current in GCP training.

10.1.9 DATA HANDLING AND RECORD KEEPING

10.1.9.1 DATA COLLECTION AND MANAGEMENT RESPONSIBILITIES

Ongoing processing and data collection is the responsibility of the clinical trials manager and research staff under the supervision of the principal investigator. The PI is responsible for ensuring the accuracy, completeness, legibility, and timeliness of the electronic medical record data reported (Epic Systems Corporation) regarding pre-biopsy serology and any recent imaging of the prostate. The clinical trials manager is responsible for ensuring the accuracy, completeness, legibility, and timeliness of the study visit data reported.

All source documents will be completed in a neat, legible manner to ensure accurate interpretation of data. The FACT-P questionnaire will be administered in paper form, for data entry into the OnCore® data management system. All paper forms will be coded with subject number; no personally identifiable information will be associated with these forms, kept in each study participant's record and stored in a locked file cabinet. All other clinical trial data (adherence, safety, anthropometrics, demographics) will be collected in real-time using OnCore®. The OnCore® system is encrypted, includes password protection and internal quality checks, such as automatic range checks to identify data that appear inconsistent, incomplete, or inaccurate.

Only the PI and study staff at the study's data coordinating center (Yale School of Medicine/New Haven) site will have access to the participant's study records. Additionally, all specimens collected will be coded with subject number so that no personally identifiable information will be associated with the

specimens. Upon receipt of the samples for laboratory analysis of secondary endpoints telomere length, cell cycle progression of PCa mRNA, and markers of PCa tissue microarrays, the samples will be coded with the subject number (without PHI) before transfer to the laboratory on the Yale campus of co-investigators responsible for these analyses. The link between the participant's code/ID # and PHI will be kept in the clinical trial manager's locked file cabinet.

In order for the PI and/or Clinical Trials Manager to receive surgical pathology reports of [name] patients at SCH (*biopsy report*: to obtain CAPRA score variables – needed for randomization, and *prostatectomy report*: to obtain CAPRA-S post-surgical score variables – a secondary outcome measure), [name] will utilize Yale's Secure File Transfer. Access to the Yale Secure File Transfer system ("Filelocker") is gained through Yale's Central Authentication Service. Filelocker allows Yale NetId users to share files with other people both inside and outside of Yale University. It is a temporary and secure storage system for sharing files and data.

10.1.9.2 STUDY RECORDS RETENTION

All documents and subject information will be strictly maintained according to the Yale IRB and HIPAA regulations to ensure confidentiality at all times. Access to subject information will be limited to a "need to know" basis and all data will be coded to maintain confidentiality. Only those investigators with appropriate Human Subjects training will have access to subject data. All data will be managed to assure strict confidentiality of participants at all times. Data will be kept for five years after the study ends. Data will then be de-identified using a "Safe Harbor" (45CFR164.514(b)(2)) approach consistent with the HIPAA Privacy rule. No records will be destroyed without the written consent of the principal investigator.

10.1.10 PROTOCOL DEVIATIONS

A protocol deviation is any noncompliance with the Yale University IRB-approved clinical trial protocol. The noncompliance may be either on the part of the participant, the investigator, or study staff. As a result of deviations, corrective and preventive actions will be developed by the principal investigator and relevant study team members and implemented promptly.

It is the responsibility of the clinical trials manager to use continuous vigilance to identify and report deviations to the principal investigator as soon as the deviation becomes known. Protocol deviations will be reported to the Yale IRB (per Yale's HRPP Procedure 700 PR.1), if the deviation is determined major (using Yale's HRPP Decision Tree 700 GD.1). All investigators and study staff are responsible for knowing and adhering to protocol and IRB requirements.

10.1.11 PUBLICATION AND DATA SHARING POLICY

This study will comply with the NIH Data Sharing Policy and Policy on the Dissemination of NIH-Funded Clinical Trial Information and the Clinical Trials Registration and Results Information Submission rule. As such, this trial will be registered at ClinicalTrials.gov, and results information from this trial will be submitted to ClinicalTrials.gov. In addition, every attempt will be made to publish results in peer-reviewed journals.

In addition, this study will comply with the NIH Genomic Data Sharing Policy, which applies to all NIH-funded research that generates large-scale human or non-human genomic data, as well as the use of these data for subsequent research. Large-scale data include genome-wide association studies (GWAS), single nucleotide polymorphisms (SNP) arrays, and genome sequence, transcriptomic, epigenomic, and gene expression data.

10.1.12 CONFLICT OF INTEREST POLICY

The independence of this study from any actual or perceived influence, such as by an industry sponsor, is critical. Therefore, any actual conflict of interest of persons who have a role in the design, conduct, analysis, publication, or any aspect of this trial will be disclosed and managed. Furthermore, persons who have a perceived conflict of interest will be required to have such conflicts managed in a way that is appropriate to their participation in the design and conduct of this trial. Yale University has established policies and procedures to disclose all conflicts of interest, and has a mechanism in place for the management of all reported dualities of interest by requiring conflict of interest disclosure reporting prior to protocol approval (and annually), for every individual listed on the protocol.

10.2 ADDITIONAL CONSIDERATIONS

In addition to the Yale University IRB, approval for the clinical trial protocol was received from the Yale Cancer Center Protocol Review Committee, on March 20, 2017.

10.3 ABBREVIATIONS

AE	Adverse Event
ANCOVA	Analysis of Covariance
CAPRA	Cancer of the Prostate Risk Assessment
CAPRA-S	Cancer of the Prostate Risk Assessment Post-Surgical
CFR	Code of Federal Regulations
CMC	Chemistry, Manufacturing and Controls
CMP	Clinical Monitoring Plan
COC	Certificate of Confidentiality
CONSORT	Consolidated Standards of Reporting Trials
CRF	Case Report Form
CTCAE	Common Terminology Criteria for Adverse Events
CTSA	Clinical and Translational Science Award
DHHS	Department of Health and Human Services
DSMC	Data Safety Monitoring Committee
eCRF	Electronic Case Report Form
FACT-P	Functional Assessment of Cancer Therapy – Prostate
FDA	Food and Drug Administration
FFR	Federal Financial Report
GCP	Good Clinical Practice
GLP	Good Laboratory Practices
GMP	Good Manufacturing Practices
GRAS	Generally Recognized as Safe
GWAS	Genome-Wide Association Studies
HIC	Human Investigation Committee

HIPAA	Health Insurance Portability and Accountability Act
HRPP	Human Research Protection Program
ICH	International Conference on Harmonisation
IND	Investigational New Drug Application
IP	Investigational Product
IQR	Interquartile Range
IRB	Institutional Review Board
ISM	Independent Safety Monitor
ITT	Intention-To-Treat
LMH	Lawrence+Memorial Hospital
MedDRA	Medical Dictionary for Regulatory Activities
NCT	National Clinical Trial
NIH	National Institutes of Health
OHRP	Office for Human Research Protections
PCa	Prostate Cancer
PI	Principal Investigator
QA	Quality Assurance
QC	Quality Control
RCT	Randomized Controlled Trial
SAE	Serious Adverse Event
SAP	Statistical Analysis Plan
SCH	South County Hospital
SMC	Safety Monitoring Committee
SOA	Schedule of Activities
SOP	Standard Operating Procedure
UP	Unanticipated Problem
YNHH	Yale-New Haven Hospital

1 STATISTICAL CONSIDERATIONS

Due to premature study termination (inability to enroll full sample size; indicated n and percent of target), the statistical analyses focused on the primary efficacy endpoint(s). Given the final sample size, it was deemed inappropriate to undertake full statistical analyses for the secondary outcomes. Instead, baseline, end of study and difference since baseline values were reported using the approach indicated in 1.1.1.

1.1.1 GENERAL APPROACH

Categorical data will be presented as counts and percentages. Continuous variables will be presented using mean with standard deviation and median with IQR. Graphical presentations will also be made as appropriate.

Two-tailed, Type I error of 0.05 and 95% Confidence intervals will be used in analyses.

The CAPRA score level (low/medium vs high) will be used to run a stratified primary outcome analysis. Other variables will be considered later in the SAP for use as covariates in subsequent analyses. Normality of distributions of continuous variables will be assessed and transformations (e.g. log, square root) will be considered, as appropriate, to normalize not normal distributions. In the event that normality cannot be achieved, nonparametric tests will be employed.

1.1.2 ANALYSIS OF THE PRIMARY EFFICACY ENDPOINT(S)

The primary outcome is change in serum PSA. This is the difference between the PSA value at baseline and the value at the time of admission for surgery (prostatectomy).

‘Baseline’ is defined as the date that an eligible participant enrolls in the trial; randomization will occur within 3 days of baseline assessment. If no measurement is available in this 3-day window, the first measurement after randomization BUT before the date of treatment initiation and up to day 7, will be defined as baseline.

Repeated measures analysis or linear mixed models analysis will be used to assess whether the mean change in PSA from pre to post-treatment differs in the two groups. This can be achieved by measuring the (time by group) interaction term in a repeated measures ANOVA.

In secondary analysis of the primary outcome, the difference in PSA mean level at post-intervention/pre-surgery between the two groups will be assessed using ANCOVA and adjusting for pre-intervention/baseline values. This analytical approach will test whether the QC group has a higher PSA mean level following treatment. Adjusting for pre-treatment/baseline PSA level ensures that any post-treatment differences are a consequence of treatment, and not a result of some random effect from the pre-treatment differences between the groups. In addition, variation in the post-treatment means stemming from the variation introduced from the pre-treatment participant starting point.

Stratified analysis (low/medium vs. high CAPRA score) will also be carried out.

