6.3 MEASURES TO MINIMIZE BIAS: RANDOMIZATION AND BLINDING

Description of randomization and blinding procedures: A single randomization scheme for the study will be generated. This scheme will be written and validated by a system programmer in the Medical Informatics Group, Yale Center for Clinical Investigation (YCCI)/NIH CTSA, and will be incorporated into Yale's Clinical Trial Management System, OnCore®. Participants will be randomized to one of two arms, intervention or placebo control (n = 72; allocated in a 1:1 ratio to 36 per arm). Allocation will be concealed through restrictions within the OnCore® system, where neither the block nor block size can be revealed to study personnel. The randomization scheme is stratified by risk level (0-4 = low/intermediate risk, 5-10 = high risk), which is based on the Cancer of the Prostate Risk Assessment (CAPRA) score. Once made, the assignment is final and the participant will be analyzed in that group regardless of future events or information, in accordance with the intent-to-treat principle.

Plans for the maintenance of trial randomization codes and appropriate blinding: After review of eligibility criteria, the blinded clinical trials manager will access the OnCore® system to enter the participant's screening/baseline data and indicate study eligibility status, thus initiating randomization. Once a participant's study status is updated to "Eligible", this indication will then be retrieved by a blinded, specified OnCore® statistician who will perform the randomization assignment through OnCore®. The statistician will also serve as liaison to the dispensing pharmacy by sending confirmation via email to either the Yale-New Haven Hospital pharmacists or the South County Hospital pharmacist, informing them of the randomization event, in order for them to release the order for preparing the assigned IP for dispensing. The statistician will also inform the clinical trials manager when a participant has been randomized, giving an indication when the IP may be obtained from the pharmacy. The YNHH and SCH pharmacists will be necessarily unblinded to participant's randomization status. LMH pharmacists, however, will remain blinded; YNHH pharmacy will simply currier the kits needed for subject visits at LMH.

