8 STUDY ASSESSMENTS AND PROCEDURES

8.1 EFFICACY ASSESSMENTS

Sequence of events to occur during the screening process and any decision points regarding participant eligibility: Positive post-biopsy prostate cancer patients of the PI and other Yale School of Medicine referring urologists will be invited to participate in the study. The patients will be identified to the clinical trials manager, who will invite them to meet in person for clinical screening at the Yale Center for Clinical Investigation's outpatient research clinic, the CSRU (Church Street Research Unit), or LMH's or SCH's urology clinic area (determined by referring physician's location), as they await prostatectomy. An initial phone screening will take place to first, to assess the patient's interest in participating, discuss study details, and determine whether any unknown exclusion criteria exist before scheduling the screening visit. The referring urologist determines their patients' eligibility for study entry at time of referral.

Time frame prior to enrollment within which screening procedures/evaluations must be performed: The Screening/Baseline Visit will take place as soon after the patient's prostatic biopsy as possible. Ideally, study enrollment will occur within 3-4 days after the Screening/Baseline Visit, as patients will have been given their date for prostatectomy, and the interim between biopsy and surgery is the period of the intervention.

In the event a randomized patient's prostatectomy is postponed (whether by patient preference or otherwise) beyond 180 days from the initial Screening/Baseline visit, the patient must be re-screened to have new baseline laboratory values established if he wishes to resume participation in the study.

Procedures and evaluations to be done as part of the study to support the determination of efficacy include:

- **Biological specimen collection and laboratory evaluations** – Screening/baseline and end-of-study serology (final study visit, Visit 2 - time of admission for surgery, 24 hours after ingestion of the last study dose) includes:

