9.3 POPULATIONS FOR ANALYSES

Intention-to-treat ('as randomized') analyses will be performed on all randomized participants. Duration of treatment will be taken into account in the analysis.

Per-protocol ('as-treated') analysis will also be carried out; assessment of treatment adherence will be based on self-reported reporting during phone follow-up calls.

The Safety Analysis dataset will include participants who took at least one dose of study medication.

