9.4.2 ANALYSIS OF THE PRIMARY EFFICACY ENDPOINT(S)

The primary outcome is change in serum PSA. This is the difference between the PSA value at baseline and the value at the time of admission for surgery (prostatectomy).

'Baseline' is defined as the date that an eligible participant enrolls in the trial; randomization will occur within 3 days of baseline assessment. If no measurement is available in this 3-day window, the first measurement after randomization BUT before the date of treatment initiation and up to day 7, will be defined as baseline.

Repeated measures analysis or linear mixed models analysis will be used to assess whether the mean change in PSA from pre to post-treatment differs in the two groups. This can be achieved by measuring the (time by group) interaction term in a repeated measures ANOVA.

In secondary analysis of the primary outcome, the difference in PSA mean level at post-intervention/pre-surgery between the two groups will be assessed using ANCOVA and adjusting for pre-intervention/baseline values. This analytical approach will test whether the QC group has a higher PSA mean level following treatment. Adjusting for pre-treatment/baseline PSA level ensures that any post-treatment differences are a consequence of treatment, and not a result of some random effect from the pre-treatment differences between the groups. In addition, variation in the post-treatment means stemming from the variation introduced from the pre-treatment participant starting point.

Stratified analysis (low/medium vs. high CAPRA score) will also be carried out.

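### The primary PSA test is valid but amounts to a change-score t-test; making the planned baseline-adjusted ANCOVA, with the CAPRA stratum, primary would usually be more precise at almost no cost.

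*SAP*

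**What the plan says.** Protocol 9.4.2 and SAP 1.1.2 carry the same text. The primary outcome is PSA at admission for surgery compared with PSA at baseline. The method is left as one of two: "Repeated measures analysis or linear mixed models analysis will be used to assess whether the mean change in PSA" from before to after treatment differs between arms. The SAP then adds: "This can be achieved by measuring the (time by group) interaction term in a repeated measures ANOVA".

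Baseline adjustment comes next, labelled a secondary analysis of the primary outcome: the post-treatment difference in means "will be assessed using ANCOVA and adjusting for pre-intervention/baseline values".

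CAPRA level is a design factor. Protocol 6.3 states: "The randomization scheme is stratified by risk level". Its place in the analysis is described in two ways. SAP 1.1.1 says: "The CAPRA score level (low/medium vs high) will be used to run a stratified primary outcome analysis". SAP 1.1.2 closes with: "Stratified analysis (low/medium vs. high CAPRA score) will also be carried out".

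Protocol 9.3 adds: "Duration of treatment will be taken into account in the analysis". It gives no term or method, and the SAP text does not mention duration.

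SAP section 1 reports that the trial ended before reaching its target and that full analysis was confined to the primary endpoint.

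**The concern.** The change score fixes the coefficient of baseline PSA at 1, whereas ANCOVA estimates it. When the pre/post correlation is below 1 and the visit variances are similar, the estimated slope gives a smaller variance for the treatment effect. The plan gives a rationale for baseline adjustment in SAP 1.1.2 but leaves it out of the primary test.

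The two sentences on CAPRA do not settle whether the stratum is a model term, a pooled stratified estimate or two separate within-stratum analyses. Randomization was stratified on CAPRA, so a reader would expect it in the primary model.

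What is at stake is the width of one confidence interval. With the trial cut short, that comparison is the only one given full inference, and both baseline PSA and CAPRA are already collected.

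**Working it through.** **Inputs.** Difference 15, SD 20.3, two-sided alpha 0.05, power 0.8 (Protocol 9.2); 36 per arm (Protocol 6.3). Neither the pre/post correlation rho nor the achieved N is given. I take rho = 0.5, 0.8 and 0.9, and total N = 72, 36 and 20; the last two are assumed values.

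**The plan's own figure.** 2 × (20.3 × (1.960 + 0.842)/15)² = 28.75, so 29 per arm by the normal formula, and 30 per arm with the t distribution. The stated 36 per arm gives 87% power. An unstated allowance or correlation would explain the gap. That is a separate matter, and nothing below depends on it.

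**Step 1: what the primary test is.** On one simulated complete data set with 36 per arm, the change-score t² was 2.4513, the repeated measures interaction F was 2.4513 and the random-intercept mixed-model z² was 2.4513. They are the same test.

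**Step 2: is it valid?** Simulated type I error of the unadjusted change-score test, with the stratum balanced (assumed 24 and 12 per arm), was 0.051 with no stratum effect, 0.049 with a moderate effect, and 0.030 and 0.018 with strong effects. Leaving out the stratum makes the test conservative, not liberal.

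**Step 3: variance ratio.** With equal visit variances s²:
- change score: 2(1 − rho)s²
- ANCOVA: (1 − rho²)s²
- ratio: (1 + rho)/2

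Estimating the baseline slope costs a factor. With CAPRA balanced by stratified randomization, the stratum adds no second inflation and costs about one degree of freedom. The factor is then about 1 + 1/(N − 4), with N − 4 residual degrees of freedom against N − 2:
- N = 72: 1 + 1/68 = 1.015
- N = 36: 1 + 1/32 = 1.031
- N = 20: 1 + 1/16 = 1.0625

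A simulation at 10 per arm (15,000 runs per cell, about a third of each arm high risk, CAPRA balanced) gave ratios of 0.80, 0.94 and 1.01. The formula gives 0.80, 0.96 and 1.01.

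**Step 4: power (noncentral t), with 20.3 as the SD of change.** Example at N = 72, rho 0.5. The change-score SE is 20.3 × √(2/36) = 4.785, and 15/4.785 = 3.135 on 70 df gives 87.1%. The ANCOVA ratio is 0.75 × 1.0147 = 0.761, so the SE is 4.785 × √0.761 = 4.174, and 15/4.174 = 3.594 on 68 df gives 94.3%.

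| Per arm | Change score | ANCOVA + CAPRA, rho 0.5 / 0.8 / 0.9 | Variance ratio |
|---|---|---|---|
| 36 | 87% | 94% / 90% / 88% | 0.76 / 0.91 / 0.96 |
| 18 | 58% | 69% / 61% / 58% | 0.77 / 0.93 / 0.98 |
| 10 | 35% | 41% / 36% / 34% | 0.80 / 0.96 / 1.01 |

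**Step 5: break-even.** The variances are equal at rho = 2/factor − 1, which is about 0.97, 0.94 and 0.88 at N = 72, 36 and 20.

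**Sensitivity to the meaning of 20.3.** If it is the SD at one visit, the SD of change is 20.3 × √(2(1 − rho)). At rho 0.5 that is again 20.3 and the figures above hold. At rho 0.8 or more, both tests exceed 99% power at 36 per arm and the choice no longer matters for power.

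**The case against.** The strongest reply is that nothing here is wrong. The test holds its type I error, ANCOVA is already planned, and a CAPRA-stratified analysis of the primary outcome is already promised, so only the order of two prespecified analyses is in dispute. This stands in part: the point is one of efficiency and clarity. The order still decides which interval is the trial's primary result.

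The past tense of SAP section 1 suggests that the analysis has been run. If so, the precision argument cannot justify changing the primary. This stands, and it limits the fix.

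The equivalence depends on how the text is read. The SAP permits a mixed model and says only that the interaction can be used. A mixed model that constrains the baseline means to be equal would be baseline-adjusted, and with missing Visit 2 PSA a mixed model can differ from the t-test. Both are fair, and they are reasons to name the model.

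A reader might infer three stronger things that the documents do not support:
- **That the primary result would be biased or have inflated type I error.** Step 2 shows otherwise.
- **That the outcome scale is undefined.** Protocol 9.1 and SAP 1.1.2 define a difference. Only the normality and transformation clause (Protocol 9.4.1, SAP 1.1.1) leaves the scale open.
- **That adding CAPRA makes ANCOVA clearly worse in a small trial.** That would treat CAPRA as a covariate balanced only by chance, whereas Protocol 6.3 stratifies on it.

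**Conclusion.** The point holds as an efficiency improvement, not as an error. As described, the primary test with complete data is a change-score t-test. ANCOVA with baseline PSA and CAPRA has smaller variance unless rho exceeds about 0.97, 0.94 or 0.88 at N = 72, 36 or 20. At moderate rho the gain is useful: 7 percentage points of power at 36 per arm and about 11 at 18 per arm, both at rho 0.5. At rho 0.9 it is a point or less at 36 and 18 per arm, and at 10 per arm there is a very slight loss.

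These figures assume equal visit variances, CAPRA balanced between arms and adding nothing beyond baseline PSA, and 20.3 as the SD of change on the analysis scale. The values of rho and the achieved N are assumptions. The handling of duration and the form of the CAPRA analysis are minor gaps in detail.

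**What to change.** **If the data are still blinded:** make ANCOVA of Visit 2 PSA on arm, baseline PSA and CAPRA stratum the primary analysis, on one scale fixed in advance. A log scale would change the estimand from a difference to a ratio, so that choice must be stated as such. Keep the time-by-group interaction as a sensitivity analysis.

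**If the data are unblinded:** keep the stated primary, say which model and scale were used, report the planned ANCOVA with its confidence interval beside it, and label any switch post hoc.

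**Minor clarifications in either case:** say whether the CAPRA-stratified analysis is pooled or stratum-wise, and how duration of treatment enters. If duration is a covariate, the interval to scheduled surgery is preferable to observed duration, which is post-randomization. Protocol 8.1 says that at enrollment "patients will have been given their date for prostatectomy", though it also allows for postponement.

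**Cost:** SAP wording, two residual degrees of freedom and a variance factor of about 1.01, 1.03 and 1.06 at N = 72, 36 and 20. If blocks are left incomplete and CAPRA is not fully balanced, the factor lies between those values and 1.03, 1.06 and 1.13. No extra patients or data are needed.
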